**** Alternative immunosuppressant trough level only if applicable**

5-Year Follow-Up

Subjects who complete the original 52-week post-transplant evaluation period will be asked to continue follow-up evaluations every three months for five years for safety and efficacy monitoring. All subjects can voluntarily withdraw from follow-up at any time.

The following examinations and blood tests will be performed according to the *Schedule of 5-Year Follow-Up* (Section 6.7.1). Additional evaluations may be required for medical conditions presenting during the study period and according to best medical practice. Should the function of the islet graft decline over time and the subject return to insulin therapy, repeat transplant may be considered.

- History and adverse event and toxicity assessments (reviewed at each visit and recorded at any time necessary)
- Physical exam including vital signs (blood pressure, heart rate, respiratory rate, temperature)
- Body mass index (BMI, body weight in kilograms over square of height in centimeters)
- Electrocardiogram (ECG)
- Comprehensive metabolic profile (CMP):
 - Na⁺, K⁺, Cl⁻, Ca⁺⁺, CO₂, creatinine, BUN, glucose, total protein, albumin, total bilirubin, ALP, AST, ALT, amylase
- Complete blood count (CBC):
 - Hemoglobin, hematocrit, red blood cells, white blood cells, differential
- Urine analyses
 - Urinalysis
 - Creatinine, osmolality, microalbumin, total protein
 - Microalbumin-creatinine ratio)
- Drug levels
 - Tacrolimus and sirolimus, and alternative trough levels if applicable to reach target levels as defined in Section 6.5.2
- Cytomegalovirus (CMV) viral load by real time PCR
- Epstein-Barr Virus (EBV) viral load by real time PCR
- HbA1c, basal C-peptide, fructosamine
- Blood sugar self-monitoring (BS-SM)
- Metabolic tests to evaluate insulin-secretory capacity of the islet graft:
 - IVGTT – intravenous glucose tolerance test
 - GST - glucagon stimulation test
 - OGTT – oral glucose tolerance test
 - MMTT - mixed meal tolerance test
- Detailed lipid panel:
 - Total cholesterol, direct LDL cholesterol, HDL cholesterol, triglycerides, apolipoprotein B, apolipoprotein A1, free fatty acids, and lipid fraction ratio
- Lipid panel:
 - Cholesterol, HDL, triglycerides, LDL cholesterol
- Inflammatory panel:

- CRP, MCP, MMP9, CAM, VCAM, fibrinogen, PAI-1 (antigen), TPA
- B-type natriuretic protein (BNP)
- Panel reactive antibodies (PRA)
- Antibodies: anti-GAD 65, anti-IA2, anti-islet cell, and anti-insulin
- IL2 receptor saturation
- Archive serum
- Thyroid ultrasound (annually)
- Abdominal ultrasound and Doppler
- Primary care screening referrals:
 - Women:
 - Mammography annually from age 40
 - Pap test according to current American Cancer Association guidelines
 - Men:
 - Prostate specific antigen (PSA) annually beginning at age 50
 - All subjects
 - Fecal occult blood testing (FOBT) annually
 - Dual x-ray absorptiometry scans (DXA) every 2 years
 - Skin cancer screening annually
 - Dental examination yearly
 - Vision and retina examinations annually
 - Flu vaccine annually
 - Pneumovax according to current CDC guidelines for patients with diabetes or immunocompromising conditions: At least one vaccine and a one-time revaccination if the vaccine was administered > 5 years ago

6.6.9 Schedule of 5-Year Follow-Up

Visit	1	2	3	4	5	6	7	8	9	10	11	12	13	14	15	16	17	18	19	20
Months	3	6	9	12	15	18	21	24	27	30	33	36	39	42	45	48	51	54	57	60
History, physical exam, vitals	X	X	X	X	X	X	X	X	X	X	X	X	X	X	X	X	X	X	X	X
BMI	X	X	X	X	X	X	X	X	X	X	X	X	X	X	X	X	X	X	X	X
ECG				X				X				X				X				X
CMP, direct bilirubin	X	X	X	X	X	X	X	X	X	X	X	X	X	X	X	X	X	X	X	X
CBC	X	X	X	X	X	X	X	X	X	X	X	X	X	X	X	X	X	X	X	X
Urinalysis		X		X		X		X		X		X		X		X		X		X
CMV q PCR	X	X	X	X	X	X	X	X	X	X	X	X	X	X	X	X	X	X	X	X
EBV q PCR		X		X		X		X		X		X		X		X		X		X
M/C ratio		X		X		X		X		X		X		X		X		X		X
IVGTT				X				X				X				X				X
Glucagon stimulation test				X				X				X				X				X
OGTT				X				X				X				X				X
Mixed meal test				X				X				X				X				X
HbA1c and fructosamine	X	X	X	X	X	X	X	X	X	X	X	X	X	X	X	X	X	X	X	X
Basal C-peptide	X	X	X	X	X	X	X	X	X	X	X	X	X	X	X	X	X	X	X	X
BS-SM twice weekly fasting	X	X	X	X	X	X	X	X	X	X	X	X	X	X	X	X	X	X	X	X
Detailed lipid panel				X				X				X				X				X
Inflammatory panel				X				X				X				X				X
Lipid panel		X				X				X				X					X	
BNP		X				X				X				X					X	
Archive serum		X		X		X		X		X		X		X		X		X		X
Abdominal ultrasound Doppler				X				X				X				X				X
Tacrolimus, Sirolimus	X	X	X	X	X	X	X	X	X	X	X	X	X	X	X	X	X	X	X	X
PRA				X				X				X				X				X
Antibodies				X				X				X				X				X
IL2 receptor saturation	X	X	X	X	X	X	X	X	X	X	X	X	X	X	X	X	X	X	X	X
Primary care screenings, vaccines				X				X				X				X				X
Thyroid Ultrasound				X				X				X				X				X

BMI: body mass index; Vitals: blood pressure, heart rate, temperature, weight; ECG: electrocardiogram; CMP: comprehensive metabolic profile; CBC: complete blood count; M/C ratio: microalbumin to urine creatinine ratio (random); IVGTT: intravenous glucose tolerance test; OGTT: oral glucose tolerance test; BNP: B-type natriuretic peptide; PRA: panel reactive antibodies; Antibodies: anti GAD65, anti IA2, anti islet cell, anti insulin. IL2 receptor saturation at investigator's discretion.

6.7 10-Year Follow-Up

Subjects who complete the 5-year post-transplant evaluation period will be asked to continue follow-up evaluations every three months for an additional five years for safety and efficacy monitoring. All subjects can voluntarily withdraw from follow-up at any time.

The following examinations and blood tests will be performed according to the *Schedule of 10-Year Follow-Up* (Section 6.8.1). Additional evaluations may be required for medical conditions presenting during the study period and according to best medical practice. Should the function of the islet graft decline over time and the subject return to insulin therapy, repeat transplant may be considered.

- History and adverse event and toxicity assessments (reviewed at each visit and recorded at any time necessary)
- Physical exam including vital signs (blood pressure, heart rate, respiratory rate, temperature)
- Body mass index (BMI, body weight in kilograms over square of height in centimeters)
- Electrocardiogram (ECG)
- Comprehensive metabolic profile (CMP):
 - Na⁺, K⁺, Cl⁻, Ca⁺⁺, CO₂, creatinine, BUN, glucose, total protein, albumin, total bilirubin, ALP, AST, ALT, amylase
- Complete blood count (CBC):
 - Hemoglobin, hematocrit, red blood cells, white blood cells, differential
- Urine analyses
 - Urinalysis
 - Creatinine, osmolality, microalbumin, total protein
 - Microalbumin-creatinine ratio)
- Drug levels
 - Tacrolimus and sirolimus trough levels to reach target levels as defined in Section 6.5.2
- Cytomegalovirus (CMV) viral load by real time PCR
- Epstein-Barr Virus (EBV) viral load by real time PCR
- HbA1c, basal C-peptide, fructosamine
- Blood sugar self-monitoring (BS-SM)
- Metabolic tests to evaluate insulin-secretory capacity of the islet graft:
 - IVGTT – intravenous glucose tolerance test
 - GST - glucagon stimulation test
 - OGTT – oral glucose tolerance test
 - MMTT - mixed meal tolerance test
- Lipid panel:
 - Cholesterol, HDL, triglycerides, LDL cholesterol
- B-type natriuretic protein (BNP)
- Panel reactive antibodies (PRA)
- Antibodies: anti-GAD 65, anti-IA2, anti-islet cell, and anti-insulin
- IL2 receptor saturation

- Archive serum
- Thyroid ultrasound (annually)
- Abdominal ultrasound and Doppler
- Primary care screening referrals:
 - Women:
 - Mammography annually from age 40
 - Pap test according to current American Cancer Association guidelines
 - Men:
 - Prostate specific antigen (PSA) annually beginning at age 50
 - All subjects
 - Fecal occult blood testing (FOBT) annually
 - Dual x-ray absorptiometry scans (DXA) every 2 years
 - Skin cancer screening annually
 - Dental examination yearly
 - Vision and retina examinations annually
 - Flu vaccine annually
 - Pneumovax according to current CDC guidelines for patients with diabetes or immunocompromising conditions: At least one vaccine and a one-time revaccination if the vaccine was administered > 5 years ago

6.7.1 Schedule of 10-Year Follow-up

Visit	1	2	3	4	5	6	7	8	9	10	11	12	13	14	15	16	17	18	19	20	
Months	3	6	9	12	15	18	21	24	27	30	33	36	39	42	45	48	51	54	57	60	
History, physical exam, vitals	X	X	X	X	X	X	X	X	X	X	X	X	X	X	X	X	X	X	X	X	X
BMI	X	X	X	X	X	X	X	X	X	X	X	X	X	X	X	X	X	X	X	X	X
ECG				X				X				X				X				X	
CMP, direct bilirubin	X	X	X	X	X	X	X	X	X	X	X	X	X	X	X	X	X	X	X	X	X
CBC	X	X	X	X	X	X	X	X	X	X	X	X	X	X	X	X	X	X	X	X	X
Urinalysis		X		X		X		X		X		X		X		X		X		X	
CMV q PCR	X	X	X	X	X	X	X	X	X	X	X	X	X	X	X	X	X	X	X	X	X
EBV q PCR		X		X		X		X		X		X		X		X		X		X	
M/C ratio		X		X		X		X		X		X		X		X		X		X	
IVGTT				X				X				X				X				X	
Glucagon stimulation test				X				X				X				X				X	
OGTT				X				X				X				X				X	
Mixed meal test				X				X				X				X				X	
HbA1c and fructosamine	X	X	X	X	X	X	X	X	X	X	X	X	X	X	X	X	X	X	X	X	X
Basal C-peptide	X	X	X	X	X	X	X	X	X	X	X	X	X	X	X	X	X	X	X	X	X
BS-SM twice weekly fasting	X	X	X	X	X	X	X	X	X	X	X	X	X	X	X	X	X	X	X	X	X
Lipid panel		X		X		X		X		X		X		X		X		X		X	
BNP		X				X				X				X				X			
Archive serum		X		X		X		X		X		X		X		X		X		X	
Abdominal ultrasound Doppler				X				X				X				X				X	
Tacrolimus, Sirolimus	X	X	X	X	X	X	X	X	X	X	X	X	X	X	X	X	X	X	X	X	X
PRA				X				X				X				X				X	
Antibodies				X				X				X				X				X	
IL2 receptor saturation	X	X	X	X	X	X	X	X	X	X	X	X	X	X	X	X	X	X	X	X	X
Primary care screenings, vaccines				X				X				X				X				X	
Thyroid Ultrasound				X				X				X				X				X	

BMI: body mass index; Vitals: blood pressure, heart rate, temperature, weight; ECG: electrocardiogram; CMP: comprehensive metabolic profile; CBC: complete blood count; M/C ratio: microalbumin to urine creatinine ratio (random); IVGTT: intravenous glucose tolerance test; OGTT: oral glucose tolerance test; BNP: B-type natriuretic peptide; PRA: panel reactive antibodies; Antibodies: anti GAD65, anti IA2, anti islet cell, anti insulin. IL2 receptor saturation at investigator's discretion.

6.8 Withdrawal or Discontinuation

All subjects can voluntarily withdraw from the study at any time. In addition, the Investigator may discontinue subjects from the study under the conditions noted below. Individuals who prematurely leave the study may elect to continue immunosuppressive therapy under the care of their own physicians, and at their own expense. If a subject with functioning transplanted islets chooses not to continue immunosuppressive therapy, he/she must be informed of the risk for losing the islet graft and returning to his/her original method of insulin management.

6.8.1 *When and How to Stop Sequential Transplants*

Subjects will be not receive any subsequent transplants if either no suitable donor pancreata were made available during that period or the subject has become otherwise ineligible for a second transplant. These subjects will be encouraged to remain in the study for safety and efficacy monitoring.

Subjects will be immediately withdrawn from subsequent transplants for serious and unexpected adverse experiences that appear to be related to the treatment regimen. Subjects will also be withdrawn if they are no longer willing or able to comply with the protocol.

Subjects who become pregnant during the study period will be recommended to stop immunosuppression. If a subject is unwilling to stop immunosuppression, appropriate information must be given in regard to the risk of fetal malformations with the use of immunosuppression. In any case, sirolimus needs to be stopped and replaced by mycophenolate mofetil because of lack of documented experience with the use of sirolimus during pregnancy.

Subjects who withdraw or are discontinued from subsequent transplants will not be replaced, i.e., the total number of subjects transplanted will not be more than 50

6.8.2 *Type and Timing of Data Collected from Withdrawn Subjects*

Subjects who withdraw from the study for any reason will be asked to continue follow-up evaluations on their original protocol schedule, except for unnecessary tests not related to their clinical care (e.g., monitoring of blood levels for medications no longer being taken). At a minimum, the subject's health status information will be collected so that some safety and efficacy information may be obtained through the original follow-up period.

If a subject intends to withdraw and forego further follow-up examinations, he/she will be asked to complete at least a single comprehensive examination for study exit equivalent to the final one-year evaluation, or as much of that exam as he/she is willing to complete. Documentation of a subject's decision and reason to not continue or complete requested testing will be recorded in the case report form.

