6.5.2 Immunosuppression Dosing and Administration

Participants in the trial will receive immunosuppression using agents approved by the FDA for organ transplantation and evaluated for use in human islet transplantation under IND to prevent allotransplant rejection. Subjects will receive basiliximab, sirolimus, tacrolimus, and etanercept in the immunosuppressive regimens. Subjects who are sensitized to human leukocytes will receive thymoglobulin instead of basiliximab for the initial transplant. Sirolimus and tacrolimus will be given according to the Edmonton protocol as described by Shapiro et al. (14). In addition to the medications included in the Edmonton protocol, participants will receive etanercept as proposed by the University of Minneapolis group and based on experimental data indicating that TNF alpha receptor antagonist improves Islet graft function and engraftment (27). It should be noted that under this protocol, corticosteroids are omitted from the post-transplant immunosuppressive regimen. Mycophenolate mofetil may be used for subjects who do not tolerate the adverse effects of sirolimus or tacrolimus. Other immunosuppressant medications may be used for subjects who do not tolerate the adverse effects of sirolimus, tacrolimus. or mycophenolate mofetil.

Patients presenting with preformed antibodies against human leukocyte antigens will receive a more intense induction protocol with the addition of a polyclonal anti-T-cell antibody preparation (Thymoglobulin).

Beginning with the initial transplant, a steroid free immunosuppressive regimen will be administered to all subjects. Subjects will receive initial doses of basiliximab, sirolimus, low dose tacrolimus, and etanercept according to the following schedule (see Section 6.5.4).

Basiliximab (Simulect®) Regimen

Basiliximab will be administered at a dose of 20 mg iv given within two hours before transplant, and 20 mg iv at week 2 after transplant for a total of 2 doses. If a second or third transplant occurs and no basiliximab was given in the preceding seven days, then the dosing regimen will begin at the time of transplant. If basiliximab has been administered within the past seven days, then the dose at transplant is omitted, and one dose is given two weeks after the last dose of basiliximab. Basiliximab will not be administered for the initial transplant in patients who are sensitized to human leukocytes and receive thymoglobulin.

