Rabbit anti-human thymocyte immunoglobulin (ATG) (Thymoglobulin®) Regimen

Thymoglobulin® will be administered to patients who are sensitized to human leukocyte antigens for the initial transplant only. The first dose will be 1 to 1.5 mg/kg IV given over 6 hours immediately pre-transplant. The second dose will be 1 to 1.5 mg/kg iv over 6 hours on day 1 after transplant. Three subsequent doses of 1 to 1.5 mg/kg iv over 6 hours will be given on days 2, 3, and 4 post-transplant.

Premedication will be as follows:

- Acetaminophen (Tylenol®) 650 mg po 1/2 hour before and midway through Thymoglobulin infusion
- Diphenhydramine (Benadryl®) 50 mg po 1/2 hour before and midway through Thymoglobulin infusion
- Methylprednisolone (Solu-Medrol®) 1 mg/kg iv one hour before and midway through the first Thymoglobulin infusion

Sirolimus (Rapamune®) Regimen

Sirolimus will be administered at a loading dose of 0.2 mg/kg per day po immediately pre-transplant, and continued at a dose of 0.1 mg/kg/day each morning. Subsequently, trough serum blood levels of sirolimus will be analyzed by HPLC (two times per week initially, until trough levels are stable and within target range), and the dose will be adjusted to the target range of 12-15 ng/mL for the three months following the most recent islet infusion. When a subsequent transplant occurs, the loading dose is not used, and the subject continues on the current dosing regimen. After three months following last transplant, the target serum level will be lowered to 7-10 ng/mL.

Mycophenolate Mofetil (CellCept®) Regimen

Mycophenolate mofetil may be used for subjects who do not tolerate the adverse effects of sirolimus or tacrolimus, and will be administered at a dose of 500 mg to 1500 mg bid po for the duration of islet graft functioning.

Tacrolimus (Prograf®) Regimen

Tacrolimus will be administered at a dose of 1 mg po given immediately before transplantation, and will be continued at a dose of 1 mg po given bid. As soon as 12-hour trough tacrolimus levels (IMx assay, Abbott Laboratories) are available, the dose will be adjusted to maintain target trough levels of 3-6 ng/mL throughout the study. When a subsequent transplant occurs, the subject continues on the current dosing regimen (14).

Other Immunosuppressant Medications

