9.2.3 Mycophenolic Acid (CellCept®)

Mycophenolic acid (CellCept®) is widely used concomitantly with other immunosuppressive agents to prolong the survival of allogeneic organ transplants, and is used for islet transplant patients who do not tolerate sirolimus. It is contraindicated for pregnant women because of pregnancy loss and fetal defects, and must not be used by

women who are breast feeding. The principal adverse events reported in > 20% of patients include diarrhea, leukopenia, vomiting, opportunistic infections, hypertension, anemia, leukopenia, and peripheral edema. Non-melanoma skin carcinomas and other malignancies have been reported.

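### Section 6.8.1 orders mycophenolate mofetil in place of sirolimus for a pregnant subject, although section 9.2.3 of the same protocol contraindicates it in pregnancy

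*Protocol*

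**What the plan says.** The pregnancy rule is a short paragraph in protocol section 6.8.1, under Withdrawal or Discontinuation. It has three steps.

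- The default: "Subjects who become pregnant during the study period will be recommended to stop immunosuppression".
- For a subject who declines: "If a subject is unwilling to stop immunosuppression, appropriate information must be given in regard to the risk of fetal malformations" from immunosuppression.
- A closing order: "In any case, sirolimus needs to be stopped and replaced by mycophenolate mofetil because of lack of documented experience" with sirolimus during pregnancy.

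Section 9.2.3, headed Mycophenolic Acid (CellCept), says of that drug: "It is contraindicated for pregnant women because of pregnancy loss and fetal defects". The dosing text in section 6.5.2 is headed "Mycophenolate Mofetil (CellCept®) Regimen".

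The Reporting of Pregnancy text in section 6.9.5 requires notification of the IRB and otherwise refers back to the withdrawal section for what to do. It cites that section as 6.9; in the current numbering it is 6.8.

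**The concern.** The third step is phrased as an order and opens with words that remove any condition. The drug it orders is one the protocol itself contraindicates in exactly the situation the paragraph covers. A clinician who follows 6.8.1 to the letter would start it in a woman known to be pregnant. A clinician who does not follow it departs from the protocol.

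What is at stake is patient safety alone: pregnancy loss and fetal defects, the two harms named in section 9.2.3. The malformation counselling in 6.8.1 concerns immunosuppression in general. It does not tell the subject that the specific substitute is contraindicated. Nothing here touches the primary endpoint, the sample size or the planned analyses.

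**Working it through.** No arithmetic applies. The check is a comparison of texts.

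**1. Same product?** Section 9.2.3 speaks of mycophenolic acid, section 6.8.1 of mycophenolate mofetil. Sections 9.2.3 and 6.5.2 attach the same brand name, CellCept, to the two terms. The protocol treats them as one product, so the contraindication applies to the drug that 6.8.1 orders.

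**2. What the protocol says about each drug in pregnancy.**

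| Drug | Section | Pregnancy statement | Role in 6.8.1 |
|---|---|---|---|
| Sirolimus | 9.2.1 | Fetal effect unknown; contraception advised before, during and for at least 4 months after use | Stopped |
| Mycophenolate (CellCept) | 9.2.3 | Contraindicated; pregnancy loss and fetal defects | Ordered as replacement |
| Azathioprine | 9.2.4 | Known teratogen | Not mentioned |

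The reason given in 6.8.1 for dropping sirolimus is missing experience. That reason supports the stop. It does not support a substitute for which specific harms are already on record.

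**3. Whom does it reach?** Read literally, the order covers every subject who becomes pregnant. A replacement makes sense only for someone who stays on immunosuppression, so the fair reading is a subject on sirolimus who declines the recommendation to stop. The paragraph plainly addresses that subject.

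**4. Does any other text resolve the conflict?**

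- Section 6.6.7 has new medical conditions trigger a re-evaluation for continued immunosuppression. Pregnancy is not among its examples, and it names no alternative drug.
- Section 6.9.5 requires the investigator to suspend trial treatment where needed to protect a subject from immediate danger. This is a general power and does not amend a specific order.
- The pregnancy-reporting text leads back to the section that contains the rule.
- SAP section 2.5.2 mentions mycophenolate only for intolerance of sirolimus or tacrolimus.
- The consent letter and package inserts appear as headings only and could not be checked.

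None of these corrects the instruction.

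**5. What remains if sirolimus is stopped with no replacement?** Tacrolimus is the other maintenance agent, at a low level: "the dose will be adjusted to maintain target trough levels of 3-6 ng/mL throughout the study". The peri-transplant agents are short courses. Basiliximab ends with "20 mg iv at week 2 after transplant for a total of 2 doses". Etanercept ends on day 10, and Thymoglobulin, which sensitized subjects receive instead of basiliximab at the first transplant, ends on day 4. Basiliximab and etanercept can be given again at a later transplant, but neither provides continuing cover. Graft protection may therefore rest on tacrolimus alone.

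**The case against.** The contradiction itself is hard to dispute. The stronger arguments concern likelihood, severity, and how far a remedy should go.

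**Safeguards.** Exclusion criterion 20 bars a positive pregnancy test or an intended pregnancy. Section 6.9.5 requires sterility or contraception. Serum pregnancy tests are scheduled at screening, on the waiting list, immediately before transplant, and at weeks 20 and 52. Any pregnancy goes to the IRB, which can suspend treatment or the study. This is a single-center trial in which the investigator is the sponsor, and the contraindication stands in the investigator's own protocol. All of this stands, and it makes actual harm unlikely. It does not change what 6.8.1 orders once a pregnancy has occurred, which is the only time the paragraph is used.

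**Severity.** A rare case with no statistical consequence could be called a lesser correction. Against that, the order is mandatory and the named harms are serious. Rarity limits how often the rule would apply, not what it would do.

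**Remedy and cost.** Deleting one clause and barring the start of mycophenolate in pregnancy cures the inconsistency; further text is optional. That is right, and the fix below separates the two. It is also right that loss of graft protection is not trivial for these subjects. They entered with severe hypoglycemia and reduced awareness despite intensive insulin, and graft loss would return them to insulin management.

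**Conclusion.** The concern holds, with high confidence. Section 6.8.1 is wrong as written: for a pregnant subject who stays on immunosuppression, it orders a drug that section 9.2.3 contraindicates in pregnancy. It must be corrected on safety grounds.

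The size cannot be expressed as a number. The documents give no pregnancy rate and no sex mix, and the case needs a pregnancy despite the safeguards, current sirolimus use, and refusal of the recommended stop. It should be rare.

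The conclusion rests on two readings: that CellCept denotes the same product in both sections, and that the replacement applies to a subject who continues immunosuppression. The instruction to stop sirolimus is not in dispute.

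**What to change.** Amend the pregnancy paragraph in section 6.8.1. Two changes are needed.

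1. Keep the instruction to stop sirolimus and delete the ordered replacement.
2. State that mycophenolate is not to be started in a pregnant subject.

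Three additions are advisable but not needed to remove the contradiction.

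3. Say that mycophenolate already in use is to be stopped or reviewed, since 6.5.2 allows it for intolerance of sirolimus or tacrolimus.
4. Say that any alternative regimen is decided case by case, with transplant and obstetric input. Azathioprine should not become the default, given section 9.2.4.
5. Extend the existing graft-loss disclosure. Section 6.8 already says that a subject with functioning islets who chooses not to continue immunosuppression "must be informed of the risk for losing the islet graft and returning to his/her original method of insulin management". The same should be told to a subject who loses sirolimus without a replacement.

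The cross-reference in the pregnancy-reporting text can be corrected at the same time, and the consent form should be checked for the same instruction.

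The administrative cost is one rewritten paragraph in a protocol amendment and the consent check. The clinical cost falls on the rare subject concerned, who may be left with weaker graft protection. The amendment should say so openly.
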